# 11.5.2.1.1 Anti-HPV 16 and 18 lgG

Anti-HPV 16 and 18 IgG antibody GMCs, measured by ELISA at baseline and one month after the second dose on Month 7 (for the 0, 6-month arms), Month 13 (for the 0, 12-month arm) or Month 25 (for the 0, 24-month arm) for the two-dose Cecolin® and Gardasil® arms as well as the mixed regimen arm, will be summarize using assay-specific LLOQ/ULOQ as appropriate by arm and by trial center.

For each time point, serotype-specific GMCs will be summarized by arm as a continuous variable and corresponding 95% CIs will be provided. These results will be supplemented with a CI for the median, computed via the percentile bootstrap method, using n=10,000 replicates.

The GMC ratio and corresponding two-sided 95% CI for the comparison of a Cecolin® arms and mixed dose arm to the Gardasil® 0,6 arm will be computed.

Similarly, the GMC ratio and corresponding two-sided 95% CI for the 0,6 Cecolin® arm and 0,6 Gardasil ® arm and 24-months after the first dose will be computed.

Seroconversion rate, defined as a 4-fold rise in anti-HPV 16 and 18 IgG antibody as measured by ELISA at baseline and one month following the last dose will be summarized as a categorical variable. The type-specific difference in response proportion between the Cecolin® and mixed arms compared to the Gardasil® arm 1 month after the second dose will be computed with a corresponding 95% CI computed via the Miettinen and Nurminen score method.

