4.4.2. Method of Assigning Subjects to Treatment Groups (Randomization)

Randomization is defined as the process of assigning a subject to a study arm. Recruited and enrolled subjects will be block randomized in a 1:1:1:1:1 ratio into their assigned treatment group. Randomization will be stratified by site to balance the total subjects in each group from each site. Furthermore, since neutralization assays are labor intensive, technically more complex than Enzyme-Linked Immunosorbent Assay (ELISA) and not currently amenable to high throughput, approximately 20% of subjects from each group will be randomly selected to also participate in the Pseudovirion-based neutralization assay (PBNA) analysis.

Any enrolled subject who is randomized but withdraws for any reason prior to vaccination will be replaced. Subjects who are withdrawn for any reason after vaccination will not be replaced.

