6.4. Covariates and Subgroups

All safety analyses will be presented by group, site, and overall. All immunogenicity analyses will include adjustment for site. A sensitivity analyses of all immunogenicity data with an adjustment for baseline concentration or titer on the log scale will be conducted if 10% or more subjects are seropositive at baseline. Additionally, if 10% or more subjects are seropositive at baseline descriptive summaries of immune response among baseline seropositive and seronegative subjects will be generated.

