6.7. Multiple Center Studies

There are 2 sites in this study. All safety and immunogenicity results will be presented by site and overall. Statistical analyses of immunogenicity results will include adjustment for trial site.

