8.2. Secondary Immunogenicity Analyses

The secondary objective is to further evaluate immunogenicity of Cecolin® and Gardasil® based on HPV IgG antibody levels and to evaluate immunogenicity based on PBNA.

The primary summary of the anti-HPV 16 and 18 IgG antibody GMC and corresponding 95% CIs, measured by ELISA will be further extended to all time points and to the mixed dose arm (Table 26). GMC summaries and seropositivity rates will be repeated for each trial center (Table 27 and Table 28).

The GMC ratio and corresponding two-sided 95% CI for the 0,6 Gardasil[®] arm compared to the 0,24 mixed dose arm at one month post-second dose (Visit 6) will be calculated to assess immunogenicity of the mixed dose arm. Additionally, the GMC ratio and corresponding two-sided 95% CI for the 0,6 Gardasil[®] arm compared to the 0,6 Cecolin[®] arm at twenty-four months post-dose one (Visit 7) will be calculated to assess persistence (Table 30).

Seroconversion in anti-HPV 16 and 18 IgG antibody, defined as a 4-fold rise from baseline, will be summarized by frequency and percentage of participants per treatment group at one month after the second dose. The difference in the percentages will be computed between the Cecolin® and mixed arms compared to the Gardasil® arm one month after the second dose with a corresponding 95% CI computed via the Miettinen and Nurminen score method (Table 31). Seroconversion summaries will be repeated for each trial center (Table 32 and Table 33).

Anti-HPV 16 and 18 serum neutralizing antibody GMTs measured by PBNA and corresponding 95% CIs, will be summarized by time point and treatment group. These results will be supplemented with a 95% CI for the median (Table 35). GMT summaries will be repeated for each trial center (Table 36 and Table 37).

Graphs displaying the GMT will be created, displaying all visits and treatment groups, including overlaid data points as well as error bars denoting the 95% CI, using the appropriate log scale for the y-axis (Figure 5 and Figure 6).

Seroconversion in anti-HPV 16 and 18 measured by PBNA will be analyzed the same as anti-HPV 16 and 18 IgG antibody (Table 38).

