9.1.1. Reactogenicity

- Reactogenicity will be assessed according to immediate (at least 30 minutes post-vaccination) and • delayed reactogenicity (through Day 7), after any and each vaccination. Delayed and immediate solicited AEs will be summarized by category (local/systemic), by reaction and by postvaccination time point, overall and by site (Table 48 through Table 59). Solicited AEs will also be summarized by severity within reaction and within category by post-vaccination time point and by site and by vaccine type (Table 60 through Table 69), and by severity and reaction according to post-vaccination day by post-vaccination time point and by site. The summaries will present each severity up to the maximum severity reported for each reaction/day combination (Table 70 through Table 75). Each subject will be counted only once under the maximum severity of each reaction and/or category, where relevant, in these summaries. Analyses involving severity will include those graded ≥ 2 . Summaries of solicited AEs observed across the solicitation period will be accompanied by a two-sided Fisher exact test p-value for a difference among groups, for both local and systemic events (overall and by reaction), as well as across these events (overall). Reactogenicity events ongoing at 7 days post-vaccination will be listed (Listing 12). Duration of reactogenicity events will be summarized by reaction and time period and by site (after any dose, after first dose and after second dose) (Table 76 through Table 81).
- Measured injection site features will be summarized by group and post-vaccination time point, including but not limited to erythema/redness, swelling, and induration (Table 82 through Table 85).

Individual listings of solicited AEs ongoing at 7 days after any dose will be generated (Listing 12).

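### The overall seroconversion difference is specified without strata although the plan requires site adjustment of every immunogenicity analysis; separately, the pooled Fisher test for solicited AEs would be better stratified by site

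*SAP*

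**What the plan says.** **Design.** SAP 4.4.2: "Randomization will be stratified by site to balance the total subjects in each group from each site". No other stratification factor is named. SAP 6.7: "There are 2 sites in this study".

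**The rule.** SAP 6.4: "All immunogenicity analyses will include adjustment for site". SAP 6.7: "Statistical analyses of immunogenicity results will include adjustment for trial site". Protocol 11.5.1.1 likewise requires adjustment for centre, and protocol 11.5.2.1 carries the same methods over to the secondary objectives.

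**The method text.** SAP 8 puts trial centre as a covariate in the log-scale GMC/GMT models, and SAP 8.3 puts country in the exploratory kinetics model. For seroconversion, SAP 8.2 compares the Cecolin and mixed arms with Gardasil "with a corresponding 95% CI computed via the Miettinen and Nurminen score method" (Table 31). PBNA seroconversion is to be handled the same way (Table 38). Protocol 11.5.2.1.1 has the matching text: "corresponding 95% CI computed via the Miettinen and Nurminen score method". None of these places mentions strata or weights. Seroconversion summaries are repeated within each centre (Tables 32 and 33).

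**Solicited AEs.** SAP 9.1.1 has summaries "accompanied by a two-sided Fisher exact test p-value for a difference among groups", again with no strata. For safety, SAP 6.4 and 6.7 promise results shown by site and overall. They do not promise adjustment.

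**The concern.** A programmer who follows SAP 8.2 literally would produce a pooled two-sample interval for Tables 31 and 38, which is not what 6.4, 6.7 and protocol 11.5.1.1 require. The by-site tables do not supply an adjusted overall difference.

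Two things are at stake. First, randomisation balances site at entry but not in the analysed set. The per-protocol set is rebuilt by HPV type and time point, the arms are compared at Months 7, 13 and 25 and so face different lengths of loss, and protocol Appendix III has a Ghana-only route to missed clinic visits. If the site mix drifts apart between arms, a pooled difference mixes a site effect with the vaccine effect. Second, leaving the choice open lets it be made after data are seen in an open-label trial.

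For solicited AEs the issue is sensitivity. A pooled test of arms that were balanced by site uses too large a variance when the sites' event rates differ, so it is less able to show a difference between groups.

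**Working it through.** **The plan's own figure.** Inputs from SAP 5: margin 0.5 (0.301 on log10), SD 0.65, one-sided alpha 0.0083, 95% power per type, 10% seropositive, 15% dropout.

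- n = 2 × 0.65² × (2.394 + 1.645)² / 0.301² gives 153 evaluable per arm.
- 153 / (0.90 × 0.85) = 200 randomised, within 3% of the stated 205.
- 205 × 0.90 × 0.85 = 157 evaluable, with power 95.6% per type and 91.4% for both.

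The figure reproduces. It concerns the GMC ratio only, so nothing below changes it.

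**Seroconversion interval, pooled versus site-stratified.** The documents give no seroconversion rates by site, so the counts are assumptions. There are 157 evaluable per arm, split 79/78 by site in the balanced cases, and the stratified version uses Mantel-Haenszel weights. Entries are 95% CIs for the difference in percentage points.

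| Assumed data (arm v control) | Pooled | Stratified |
|---|---|---|
| Near 100% at both sites (156/157 v 156/157) | -2.94 to 2.94 | -2.90 to 2.90 |
| 100% at one site; 74/78 v 76/78 at the other | -5.26 to 2.28 | -5.39 to 2.37 |
| 100% at one site; 62/78 v 66/78 at the other | -9.20 to 3.94 | -9.38 to 3.86 |
| 78/79 v 79/79 at one site; 55/78 v 60/78 at the other | -11.56 to 3.81 | -11.55 to 3.47 |
| Imbalanced: 100/100 v 85/85; 50/57 v 66/72 | -5.60 to 4.21 | -7.00 to 3.24 |

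- In the balanced rows no limit moves by more than 0.34 points. The stratified interval is wider in the second row (7.76 v 7.54 points) and third row (13.24 v 13.14), and narrower in the first (5.80 v 5.88) and fourth (15.02 v 15.37).
- In the imbalanced row the pooled estimate is 150/157 - 151/157 = -0.64. The weights are 100 × 85/185 = 45.9 and 57 × 72/129 = 31.8, so the stratified estimate is 31.8 × (-3.95) / 77.8 = -1.61. The limits move by 1.40 and 0.97 points.
- That row is a severe case. From a 103/102 split at entry, 57 of 102 retained means 44% lost at one site in one arm.
- In general, the spurious difference equals the difference in site share times the difference in site rate. A 10-point shift in share with rates of 96% and 100% gives 0.10 × 4 = 0.4 points.

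**Solicited AE test.** Five arms of 205, split 103/102 by site. Event rates by site are assumptions. A pooled Pearson test stands in for Fisher.

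With arms balanced by site, the ratio of true to assumed variance is r = mean of p(1 - p) over sites, divided by p̄(1 - p̄). The pooled statistic behaves like r × χ² on 4 df, so the true size is P(χ² > 9.488/r) = exp(-x/2) × (1 + x/2), with x = 9.488/r.

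- 20%/40%: r = 0.20/0.21 = 0.952, x = 9.96, size 4.1%.
- 10%/50%: r = 0.17/0.21 = 0.810, x = 11.72, size 2.0%.

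Simulation (10,000 runs; power for a log odds ratio of 0.5 in the two Gardasil-first arms):

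| Site rates | Size, pooled v stratified CMH | Power, pooled v stratified CMH |
|---|---|---|
| 30%/30% | 5.0% v 5.0% | 87% v 87% |
| 20%/40% | 4.1% v 4.9% | 83% v 85% |
| 10%/50% | 2.1% v 5.4% | 61% v 75% |
| 5%/70% | 0.2% v 5.0% | 13% v 56% |

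**The case against.** - **Site is not ignored.** A reader might infer that the SAP decided to drop site. The documents do not support that. By-centre seroconversion tables and by-site AE summaries are planned, the Miettinen-Nurminen method has a stratified form, and nowhere is the interval called unstratified. What stands is that 8.2 leaves the method unspecified where 6.4 and 6.7 impose a rule.
- **The Fisher test breaks no rule.** A reader might infer that it contradicts 6.4 and 6.7. It does not, because the adjustment rule covers immunogenicity only. Nor does pooling inflate type I error when arms are balanced by site. This objection stands in full, so that part is advice. An exact test also suits rare reactions.
- **The seroconversion effect is small.** A reader might infer a material bias or a gain in precision. Assumed rates of 80% and 95% with one arm at 60:40 and control at 50:50 would give 1.5 points. But protocol 1.5.2 and 1.5.3 report seroconversion at or near 100%, in women given three doses, and 1.5.2 reports higher antibody levels in two-dose girls. To leave 157 evaluable at 60:40 (94 and 63), one arm would have to lose 9% of 103 at one site and 38% of 102 at the other. Precision need not improve, as two of the four balanced examples show.
- **No decision turns on it.** The seroconversion objective is descriptive with no margin, PBNA is declared descriptive, and the GMC comparisons already carry centre. This stands and limits the weight of the point, but it does not reconcile 8.2 with 6.4 and 6.7.

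**Conclusion.** The point holds as an inconsistency of low impact. As written, SAP 8.2 and protocol 11.5.2.1.1 do not carry out the site-adjustment rule for the overall seroconversion difference in Tables 31 and 38. On assumed rates, stratifying moves the limits by less than 0.4 points with arms balanced by site, and by about 1 to 1.4 points in a severe imbalance. The benefit is protection against a drifting site mix and a method fixed in advance. Narrower intervals are not assured.

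The solicited-AE test is a separate recommendation. Its loss depends on how far the sites' event rates differ, which the documents do not say: negligible at equal rates, true size about 4% at 20%/40% and about 2% at 10%/50%. These results assume near-equal site shares, whereas protocol 6.1 allows up to two thirds of participants in one country.

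The primary GMC analysis and all stated alpha, power and sample-size figures are unaffected.

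**What to change.** **Seroconversion.** In SAP 8.2 and protocol 11.5.2.1.1, state that the overall difference and its 95% CI (Tables 31 and 38) are site-stratified Miettinen-Nurminen: a common risk difference over the two sites, with the weights named. Keep the unstratified interval for the by-site Tables 32 and 33. Limiting SAP 6.4 and 6.7 and protocol 11.5.1.1 to the GMC/GMT models would also remove the inconsistency, but gives up the protection against a changed site mix.

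**Solicited AEs (optional improvement).** In SAP 9.1.1 and protocol 11.5.2.2.2, replace or accompany the pooled Fisher test with a site-stratified exact or CMH test, and keep Fisher within site. Strata will be sparse for rare reactions, where the exact version is needed.

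**Cost.** About one sentence per section and a small programming change, with no new data. The shells for Tables 31 and 38 are not in the text reviewed, so their footnotes should be checked. SAP 6.6.1 lists Tables 31 to 38 in the interim package. If that package was run with a pooled interval, the final report should say so.

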# 11.5.2.1.2 Anti-HPV 16 and 18 serum neutralizing antibody titers

Anti-HPV 16 and 18 serum neutralizing antibody GMTs measured by PBNA on a representative subset (20%) of samples at all time points will be summarized using assay-specific LLOQ/ULOQ as appropriate by arm and by trial center.

For each time point, serotype-specific GMTs will be summarized by arm as a continuous variable and corresponding 95% CIs will be provided. These results will be supplemented with a CI for the median, computed via the percentile bootstrap method, using n=10,000 replicates.

Correlation between neutralizing antibody titers measured by PBNA and IgG antibody concentrations measured by ELISA will be summarized on the continuous scale and seroconversion agreement will be summarized.

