3.2.2. Secondary Endpoints

3.2.2.1. Secondary Immunogenicity Endpoints

- Anti-HPV 16 and 18 serum neutralizing antibody geometric mean titer measured by PBNA compared to ELISA at all time points (in a representative subset).
- Seroconversion rate, defined as a 4-fold rise in anti-HPV 16 and 18 IgG antibody as measured by ELISA, at baseline and one month following the last dose.
- Anti-HPV16 and 18 IgG antibody GMC measured by ELISA one month following the last dose of the Gardasil[®] 0-6-month two dose regimen and the Gardasil[®]-Cecolin[®] 0-24-month two dose regimen.
- Anti-HPV16 and 18 IgG antibody GMC measured by ELISA 24 months following the first dose of the Gardasil® 0-6-month two dose regimen and the Cecolin® 0-6-month two dose regimen.

The corresponding two-sided 95% CI for each metric will be computed.

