4.5.1. Immunogenicity Variables

To evaluate immunogenicity of Cecolin® and Gardasil®, anti-HPV 16 and 18 IgG antibody measured by enzyme-linked immunosorbent assay (ELISA) and anti-HPV 16 and 18 serum neutralizing antibodies measured by pseudovirion-based neutralization assay (PBNA) will be used. For each treatment group, blood will be collected for immunologic testing for the primary endpoint at one month following second dose. Additional blood collections will occur at baseline, immediately prior to the administration of the 6-month, 12-month or 24-month dose, and 24 months after the first dose in Groups 1 and 4 for noninferiority comparison.

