Correlation between neutralizing antibody titers measured by PBNA and IgG antibody concentrations measured by ELISA will be summarized on the continuous scale for anti-HPV 16 and 18 and the following three categories Cecolin only, Gardasil only, and the mixed arm with colors identify timepoints (Figure 7 and Figure 8). The Spearman correlation between ELISA and PBNA results will be computed by type and for Cecolin only, Gardasil only, and the mixed arm. Summaries will be provided by three categories Cecolin only, Gardasil only, and the mixed arm and HPV type (Table 39).

Analysis of immunological assays will be supplemented by reverse cumulative distribution (RCD) curves for each treatment group for a given visit displayed on the same plot, and different panels for different visit (Figure 9 through Figure 12). Log concentration/titer will be on the x-axis and cumulative percent will be on the y-axis.

The analyses for GMC/T and GMC/T ratio will be repeated as a sensitivity analyses based on the total vaccinated cohort utilizing SAS PROC LIFEREG (Table 42 through Table 45).

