8.3. Exploratory Immunogenicity Analyses

Immunologic bridging analyses are outside the scope of this SAP.

Exploratory analyses covered in this SAP include summaries of GMTs, GMCs, seroconversion rates and seropositivity rates at the time of the second dose (sample collected prior to the dose) and one month after the second dose. Analyses will be performed for both ELISA and PBNA. Summaries will be repeated within each of the trial centers. Spaghetti plots of the antibody and titer results will be provided by study day and treatment group (Figure 13 through Figure 16). In addition, summaries of the GMC ratio one month after the second dose between the Cecolin® schedules will be generated, where the 0, 12 group and 0, 24 group will be compared (individually) to the 0, 6 group (Table 34).

GMCs/GMTs, seroconversion and seropositive rates after a single dose of Cecolin® or Gardasil® will be summarized at multiple timepoints. Arms will contribute the following timepoints

- Arm 1 (0, 6 Cecolin®): 6-month single dose for Cecolin®
- Arm 2 (0, 12 Cecolin®): 12-month single dose for Cecolin®
- Arm 3 (0, 24 Cecolin®): 24-month single dose for Cecolin®
- Arm 4 (0,6 Gardasil®): 6-month single dose for Gardasil®
- Arm 5 (0- Gardasil® and 24- Cecolin®): 24-month single dose for Gardasil®

These summaries will be contained in Table 26, Table 31, and Table 38. Additionally, single dose comparisons at 6- months (Arms 1 and 4) and 24- months (Arms 3 and 5) will be explored via the GMC ratios (Table 34).

In addition, in each arm, for both ELISA and PBNA HPV16 and HPV18, Antibody Kinetics modelestimate GMC/GMT from mixed models for repeated measures (MMNR9) will fit to log transformation of the concentration (or titres). Each model will include subject as random effect, visit and country as fixed effects and will assume compound symmetry for the covariance structure. As all subjects in the Per-Protocol population are seronegative at baseline, visit 1 will not be included in the model and presented as below LLQ. Fitted GMC/GMT and 95% CI will be presented in Table 46, Table 47 and in Figure 17 to Figure 19. The percentage decay at 18 months post-dose 2 relative to 1 month post-dose 2 for groups 1 and 4, estimated from the model, will also be presented in Table 46 and Table 47.

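### SAP 8.2 names no visit for the PBNA–ELISA Spearman correlation; taken literally it pools three or four samples per girl, baseline included, which would inflate the coefficient

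*SAP*

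**What the plan says.** SAP 8.2 defines the coefficient by HPV type and vaccine category: "The Spearman correlation between ELISA and PBNA results will be computed by type and for Cecolin only, Gardasil only, and the mixed arm". The table follows the same two factors: "Summaries will be provided by three categories Cecolin only, Gardasil only, and the mixed arm and HPV type (Table 39". Time enters this paragraph only as point colours on the scatter plots (Figures 7 and 8).

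Nearby analyses do deal with time. In the same section the PBNA titres "will be summarized by time point and treatment group", and the reverse cumulative curves have a panel per visit. The kinetics model of SAP 8.3 has a subject random effect and drops baseline: "As all subjects in the Per-Protocol population are seronegative at baseline, visit 1 will not be included in the model". The correlation has neither provision.

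The endpoint in SAP 3.2.2.1 is neutralizing antibody "measured by PBNA compared to ELISA at all time points (in a representative subset", and that section adds: "The corresponding two-sided 95% CI for each metric will be computed".

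Repeated samples are certain. SAP 4.5.1 states: "Additional blood collections will occur at baseline, immediately prior to the administration of the 6-month, 12-month or 24-month dose". That is on top of the sample one month after dose 2 and, in groups 1 and 4, a sample at 24 months. Protocol 11.5.2.1.2 has titres "measured by PBNA on a representative subset (20%) of samples at all time points" and gives no rule for repeated samples either.

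SAP 5 calls the PBNA analyses descriptive. It counts about 200 girls overall at the relevant time points and expects a lower 95% limit above 0.6 for a Spearman correlation of 0.7 or higher.

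**The concern.** A rank correlation over pooled visits has two sources. One is whether girls who rank high on one assay at a visit also rank high on the other. The other is that both assays rise after vaccination. The endpoint is about the first; pooling with a seronegative baseline adds the second. The coefficient can then look strong when agreement within a visit is modest, and a single figure does not show agreement at each time point.

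Pooling also breaks the independence behind a simple confidence interval, because one girl supplies several pairs.

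At stake is how a descriptive secondary result is read. Two analysts following SAP 8.2 could report materially different coefficients from the same data.

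**Working it through.** **Plan's own figure.** Fisher-z lower limit: tanh(atanh(r) − 1.96·√(v/(n − 3))), with v = 1, or v = 1 + r²/2 (Bonett–Wright). At r = 0.7 and n = 200:
- v = 1: tanh(0.867 − 1.96·√(1/197)) = 0.622
- v = 1.245: 0.612

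Both exceed 0.6, so the SAP 5 statement reproduces. Protocol 11.3 gives about 20 girls per arm per site: 20 × 5 × 2 = 200, that is, one value per girl.

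**Pairs if visits are pooled.** 20% of 205 is 41 girls per arm. Samples per girl: 4 in groups 1 and 4; 3 in groups 2, 3 and 5.

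| Category | Girls | Pairs | Baseline share p |
|---|---|---|---|
| Cecolin only | 123 | 41 × (4+3+3) = 410 | 123/410 = 0.30 |
| Gardasil only | 41 | 41 × 4 = 164 | 41/164 = 0.25 |
| Mixed | 41 | 41 × 3 = 123 | 41/123 = 0.333 |

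**Pooled coefficient.** Assume that every post-dose value exceeds every baseline value in both assays, that later visits share one distribution, and that the within-visit Spearman is s. On the rank scale the variance between blocks is p(1−p)/4 and the total is 1/12, so

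pooled = 3p(1−p) + s·[1 − 3p(1−p)].

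If all baseline values are tied, as they are when below LLOQ and set to LLOQ/2 (SAP 8),

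pooled = [3p(1−p) + s(1−p)³] / (1 − p³).

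| s | Cecolin only, untied / tied | Gardasil only, untied / tied | Mixed, untied / tied |
|---|---|---|---|
| 0 | 0.63 / 0.65 | 0.56 / 0.57 | 0.67 / 0.69 |
| 0.5 | 0.82 / 0.82 | 0.78 / 0.79 | 0.83 / 0.85 |
| 0.7 | 0.89 / 0.89 | 0.87 / 0.87 | 0.90 / 0.91 |

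Example, Gardasil only at s = 0.7, untied: 0.5625 + 0.7 × 0.4375 = 0.869. At the planned 0.7 the untied inflation is 0.17–0.20. Simulation agrees with the closed forms. If 10% of baseline values sit at post-dose level, or 10% of post-dose PBNA values fall below LLOQ, the tied s = 0 range drops to about 0.52–0.65.

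**Dropping visit 1 alone.** If values before and after dose 2 separate fully, pooling them 1:1 gives 3 × 0.5 × 0.5 = 0.75 at s = 0. With an assumed rise of 1 log10 (SD 0.65) and the month-24 sample at half that rise, s = 0 gives about 0.3–0.4 and s = 0.5 about 0.64–0.69.

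**Confidence interval.** Simulated coverage of a nominal 95% interval that treats pairs as independent (visit 1 excluded, s = 0.7, Bonett–Wright variance), by assumed within-girl correlation across visits:
- 0: 0.95–0.96
- 0.3: 0.94–0.95
- 0.5: 0.91–0.93
- 0.7: 0.87–0.90

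**Precision by visit at r = 0.7** (v = 1.245 and v = 1): lower limit 0.583–0.597 at n = 123, and 0.472–0.500 at n = 41. These are planned counts before losses.

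**The case against.** The strongest reply is that per-visit analysis was meant. The endpoint refers to all time points, SAP 5 counts one value per girl, and the Table 39 shell, where visit rows would stand, is in an appendix that is not in the text available. This stands: only the prose can be shown to be silent, and nobody can say that the sponsor decided to pool.

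It is also fair that 0.56–0.69 is a bounding case. Protocol 7.2 cites good correlation between the assays, and SAP 5 plans around 0.7, where the inflation is 0.17–0.20. Full separation from baseline, including PBNA up to 24 months after one dose, is assumed rather than documented. The interval problem needs pooling, an interval that ignores clustering (the SAP names no method for this coefficient) and a sizeable within-girl correlation; at 0.3 it is negligible. Coloured plots and titres by time point would let a careful reader see the clustering.

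A reader might go further and infer any of the following, which the documents do not support:
- The SAP 5 bound is wrong. It reproduces; the lower bounds within categories contradict no stated figure.
- An all-arm estimate is missing. SAP 6.1 puts an all-participants column in summary tables by default.
- The choice of ELISA or the non-inferiority result is undermined. Protocol 7.2 rests the choice on throughput and a cited correlation, and no test or threshold uses this coefficient.

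Simply adding every visit would not do either. At visit 1, if all values sit at LLOQ/2, Spearman is undefined. At visit 4 the Cecolin category mixes month 6, 12 and 24 samples: with assumed steps of 0.3 or 0.5 log10 between them (SD 0.65) and no association within arm, visit 4 alone gives about 0.13 or 0.29.

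**Conclusion.** The gap is real and more than missing detail: on its literal wording SAP 8.2 yields a coefficient driven partly by the rise from baseline. If it is applied that way, and post-dose values exceed baseline in both assays, 0.7 within a visit would be reported as about 0.87–0.90 and 0.5 as about 0.78–0.83; ties at baseline add at most about 0.01. The loss of interval coverage depends on a within-girl correlation that the documents do not give. All of this is conditional on pooling, which Table 39 may already rule out. It is a low-priority correction to a descriptive secondary analysis.

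**What to change.** In SAP 8.2 and Table 39:
- Compute Spearman with its 95% CI separately at each post-dose visit, one record per girl, within the three categories and for all participants: visit 4, visit 6, and visit 7 (groups 1 and 4 only).
- At visit 4, where time since dose differs by arm, report the Cecolin arms separately or rank within arm. The all-participants value at that visit needs the same ranking within arm.
- At visit 1, report only the number and percentage above LLOQ on each assay, with no coefficient.
- If a pooled value is also shown, label it as pooled, exclude visit 1, and take its CI from a bootstrap that resamples girls. It may still carry part of the rise after dose 2.

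If the Table 39 shell already has visit rows, a sentence in SAP 8.2 saying so, with the visit 1 and visit 4 rules, is enough.

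Cost: wording and a few table rows; no new assays. Table 39 and Figures 7 and 8 are not in the interim output list of SAP 6.6.1, so that package does not change. The coefficients will probably be lower and the intervals wider: for 0.7 at n = 41 the expected lower limit is about 0.47–0.50.
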